Protocol For A Smartphone Based Automated Directly Observed Treatment Improves Adherence and SVR to Fixed-Dose Elbasvir and Grazoprevir in PWIDs: A Randomized Controlled Trial

People who Inject Drugs (PWIDs) constitute 60% of the approximately 5 million people in the United States infected with hepatitis C virus (HCV). Successful HCV treatment leading to sustained viral response (SVR) is associated with increased survival, but to date successful treatment of PWIDs has been limited. Treatment of PWIDs is complex due to addiction, mental illness, poverty, homelessness, lack of positive social support, poor adherence-related skills, low motivation and knowledge, and poor access to and trust in the health care system. At Albert Einstein College of Medicine, we have developed a multidisciplinary model of HCV care that integrates on-site primary care, substance abuse treatment, and HCV-related care within opiate agonist treatment clinics. To optimize HCV treatment outcomes, we have introduced directly observed therapy (DOT). In our DOT model, one daily dose of oral HCV medication is administered with methadone. However, DOT is not feasible for PWIDs who are not enrolled in methadone maintenance treatment programs, and is less effective for methadone-maintained PWIDs who do not attend the methadone clinics every day. In addition, DOT has been used for decades both to measure and maximize adherence for treatment of tuberculosis infection, but the cost and logistical complexity of administering DOT for large HCV clinical programs would be prohibitive.

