Automated DOT (a-DOT), a smartphone app that uses facial recognition software and advanced features to detect noningestion, combines the accuracy of in-person DOT with the convenience of real-time centralized data collection and monitoring. Adding a daily side effect diary to a-DOT will further allow precise tracking of timing of both medication ingestion and side effects which may be compromising adherence. Zepatier (elbasvir and grazoprevir) is a new once-daily fixe-dose combination tablet which has achieved high rates of SVR ranging from 94 to 97 percent in genotype-1 infected patients including those with HIV/HCV coinfection and renal impairment. Zepatier is administered for 12 to 16 weeks, depending on HCV genotype, prior treatment history, and the presence of certain baseline NS5A polymorphisms (1a only). By administering Zepatier via this innovative a-DOT platform, we hypothesize that PWIDs treated in real-wrold settings can be successfully treated with high rates of adherence and SVR.

In this proposed 18-month trials, 75 PWIDs enrolled in opiate agonist treatment (genotypes 1a and 1b) with chronic HCV will be enrolled over a 12-month period, and randomized to either aDOT or treatment as usual (TAU). **We will recruit PWIDs from diverse community settings include a syringe exchange program (NYHRE), federally-qualified health center (Comprehensive Health Care Center), homeless shelter (The Living Room), and a methadone maintenance treatment program (Montefiore Wellness Centers).** All patients (including treatment-experienced and HIVV/HCV coinfectd subjects) will be treated with Zepatier-based regimens as per the standard of care. Rigorous data are necessary to judge the contribution of a-DOT to the success of HCV treatment in PWIDs. By performing a randomized trial of a-DOT HCV therapy (Zepatier with and without ribavirin), we will evaluate the efficacy of a-DOT for improving HCV treatment outcomes among PWIDs.

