- 1. To determine in a randomized trial whether HCV treatment delivered via a-DOT (Zepatier with and without ribavirin) provided on-site at community treatment programs during a 12-week study period is more efficacious than self-administered HCV treatment for enhancing adherence and SVR in PWIDs.** 75 subjects will receive Zepatier will be randomized to take medications by either treatment as usual (self-administration), automated directly observed therapy (a-DOT), or a-DOT with gamification (25 subjects in each arm). Those in the a-DOT arm will be observed taking their Zepatier dose by the smart-phone based interface. We hypothesize that adherence and SVR will be higher in a-DOT versus TAU subjects, and that SVR in a-DOT arm will be equivalent to SVR seen in registration trials.
- 2. To evaluate the feasibility and acceptability of a-DOT to both participants and HCV providers in tracking longitudinal patterns of adherence and providing adherence feedback in real-time.** We hypothesize that a-DOT will be highly acceptable to both participants and medical providers.
- 3. To determine whether gaming features added to the aDOT platform enhance adherence compared to standard aDOT.** For the 25 subjects randomized to the aDOT + gamification arm, subjects will compete with other subjects within this arm for modest cash incentives. Those with highest levels of adherence measured at monthly research visits compared to their peers will earn additional incentives.

4. To determine the impact of ongoing drug use (cocaine, opiates, or benzodiazepenes) and on HCV virologic outcomes in subjects receiving Zepatier by aDOT. We hypothesize that ongoing drug use during HCV treatment will not be associated with adherence in subjects randomized to a-DOT.

B. APPROACH

B.1. Preliminary Studies

B.1.1. Overview of the research team. [name] has focused on defining optimal models of HCV care for PWIDs over the last 15 years, and is expert in treating HCV in PWIDs, methadone and buprenorphine-maintained patients, and active drug users.

Monitoring and improving adherence to antiviral therapy in real world settings requires methods that address varied challenges in treating high-risk populations. While accuracy is paramount, cost, ease of deployment, desirability, scalability, privacy, and flexibility are also important for ensuring wide-scale utility.

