B.2. Overview of study approach. In the proposed study, 75 HCV-infected genotype-1 infected PWIDs eligible for on-site HCV treatment with Zepatier will be recruited from diverse community settings, and randomized to either aDOT (n=25), aDot + gamification (n=25), or TAU (n=25). We will measure adherence with pill counts in both arms and with the a-DOT interface in the a-DOT arm. All subjects will be treated with the standard regimens for 12 weeks based on subtype, baseline NS5a polymorphisms and treatment history. For this study we will not enroll patients taking Ribavirin.

- G1a: Treatment-naïve or PegIFN/RBV-experienced without baseline NS5A polymorphisms: Zepatier for 12 weeks
- G1b: Treatment-naïve or PegIFN/RBV-experienced: Zepatier for 12 weeks

B.3. Setting: Montefiore and Einstein Division of Substance Abuse (DoSA). DoSA is a clinical, research, and teaching division of Einstein’s Department of Psychiatry and Behavioral Sciences. DoSA operates a comprehensive substance abuse treatment program providing pharmacotherapy and related services to about 4200 adults (≥ 18 years) with current narcotic addiction (typically heroin). The primary focus is treatment of opiate dependence with methadone, and the average methadone pick-up schedule is 5 times per week. At present, DoSA operates three large clinics in three Bronx communities. The treatment paradigm relies on integrating general and HCV- and HIV-related medical, substance abuse, and mental health services under one roof. Multiple RCTs have been conducted in DoSA. Both recruitment and research visits will occur at DoSA. With [name] (HCV Medical Director), participant recruitment and private office space for research visits will be ensured. We have established treatment programs and/or partnerships with three additional programs: **syringe exchange program (New York Harm Reduction Educators - NYHRE), federally-qualified health center (Comprehensive Health Care Center), homeless shelter (The Living Room), and a methadone maintenance treatment program (Montefiore Wellness Centers).**

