Subjects randomized to the a-DOT arm will be instructed on using the a-DOT platform at the baseline research visit, and will take the first dose with a-DOT smartphone device in front of the HCV provider at the treatment initiation clinical visit. Prior to ingesting each daily Zepatier dose, subjects will take a brief side effect survey on the a-DOT app which rates the severity of key side effects as none, mild, moderate or severe. If subjects do not ingest Zepatier within 2 hours of scheduled dose, they will receive a friendly reminder to take the medication. Subjects who do not ingest Zepatier within 4 hours of scheduled time will receive a call from research staff during day-time hours, and the next morning if evening dose is missed. For a-DOT subjects further randomized to the gamification feature, subjects will receive real-time feedback regarding ranking of their adherence to Zepatier as compared to their peers (unnamed) leading to friendly competition for additional modest incentives to be collected at monthly research visits. Patients will return the medication packs (including any uningested tablets) at all research visits. Standard clinical visits include 2 baseline visits, and week 0, 2, 4, 8, 12, and follow up 12, and follow up 24. Additional clinical visits are scheduled as needed by either provider or patient. HCV-related labs (including LFTs) are drawn prior to each of these clinical visits as per our standard clinical protocol. In particular, hepatic laboratory testing will be performed prior to therapy, at treatment weeks 8 and 12, and as clinically indicated. Patient are instructed to consult their HCV provider without delay if they have onset of fatigue, weakness, lack of appetite, nausea and vomiting, jaundice, or

IRB NUMBER: 2016-7215
IRB APPROVAL DATE: 02/16/2018

discolored feces. HCV providers will discontinue Zepatier if ALT levels remain persistently greater than 10 times the ULN, or if ALT elevation is accompanied by signs or symptoms of liver inflammation or increasing conjugated bilirubin, alkaline phosphatase, or INR. Patients with decompensated cirrhosis (Child-Pugh B or C) will not be eligible for treatment with Zepatier.

B.9. Data sources and collection.

B.9.1. Overview. Sources of data will include: medical charts, pharmacy database and packaging (biweekly packs)

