B.9.6. Subject Compensation. Subjects will receive \$25 for each research visit and \$10 for each returned blister pack. Subjects randomized to the a-DOT arm (n=50) will receive additional incentives based on adherence measured at monthly visits: \$10 for 50% adherence; \$20 for 80% adherence; and \$30 for 95% adherence. For the subjects further randomized to the a-DOT + gamification intervention, the second-most adherent participant will receive an additional \$35 incentive, while the top-most adherent patient will receive a \$50 incentive at their subsequent study visit. Should the top two participants be tied, the participant with the most adherent time of dosing will be awarded the first-place prize. In total, participants may earn up to \$453, including metrocards and incentives.

B.9.7. Data Management/Confidentiality. Data will be stored with study ID codes in locked filing cabinets, separate from name-based files, which will be stored in a different locked cabinet. All study information and name-based information will be kept in separate, password protected, HIPAA compliant REDCap databases online. All name-based information will be destroyed at the end of the study, while study-ID-based information will be deleted if participants decline to allow storage of their records for future research of 50 years. All participants will be informed of the data management and confidentiality plan at the time of consent to participate.

B.10. Analytic plan.

First, the success of randomization will be checked by comparing the a-DOT and TAU groups on key variables, such as age, gender, race, HCV viral load, advanced liver disease, psychiatric, and active drug use. Continuous variables will be compared between study arms using the Student's t or Wilcoxon test, and

categorical variables will be compared using chi-square or Fisher's exact tests. Variables that are not equally distributed will be included in multivariate models if they are also associated with the study outcome.

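### Both a-DOT arms are paid for adherence and TAU is not, yet the payment is not named as part of the intervention, so a difference from TAU cannot be credited to a-DOT alone

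*Combined protocol and SAP*

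**What the plan says.** **Payment.** B.9.6 (Subject Compensation) pays every subject USD 25 per research visit and USD 10 per returned pack. It then adds: "Subjects randomized to the a-DOT arm (n=50) will receive additional incentives based on adherence measured at monthly visits". The tiers are USD 10, 20 and 30 for 50%, 80% and 95% adherence. The n=50 is both a-DOT arms together (25 plain, 25 with gamification, per B.2). Rank prizes of USD 35 and 50 are a further layer for the gamification arm only.

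**Definition of the intervention.** Aim 1 defines a-DOT as observation of the dose through the smartphone. B.8 adds a side-effect survey, reminders and staff calls. Where these sections mention incentives, they do so only for gamification: in Aim 3, "subjects will compete with other subjects within this arm for modest cash incentives", and in B.8, feedback on ranking "leading to friendly competition for additional modest incentives to be collected at monthly research visits".

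**Intended inference.** The title reads "Smartphone Based Automated Directly Observed Treatment Improves Adherence and SVR to Fixed-Dose Elbasvir and Grazoprevir in PWIDs". The introduction says "Rigorous data are necessary to judge the contribution of a-DOT to the success of HCV treatment in PWIDs". Aim 1 says "We hypothesize that adherence and SVR will be higher in a-DOT versus TAU subjects". B.10 concedes low power for SVR but plans to take an effect size into later funded studies of a-DOT's efficacy. It does not mention the tiered payment.

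**The concern.** Two things differ between a-DOT and TAU: the app, with its reminders and calls, and a cash reward for being adherent. The reminders and calls belong to a-DOT as B.8 describes it. The cash is a separate co-intervention aimed directly at the outcome, and its USD 20 tier sits at the same 80% level that B.10 uses to classify a subject as adherent.

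A reader who follows the title, Aim 1 and B.10 would credit any adherence or SVR difference to a-DOT. A later trial of a-DOT without payment, sized on that difference, would rest on an effect this trial does not estimate.

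There is also a conditional measurement problem. B.9.6 does not say which measure scores the tiers. If it is pill count, only a-DOT subjects have a cash motive to return emptier packs, and pill count is the adherence measure common to all arms. SVR is a laboratory result and is not open to that problem.

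**Working it through.** **1. Can any arm or contrast separate app from cash?**

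| Arm | App | Tiered cash | Rank prizes |
|---|---|---|---|
| TAU (n=25) | no | none described | no |
| a-DOT (n=25) | yes | yes | no |
| a-DOT + gamification (n=25) | yes | yes | yes |

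The app and tier columns are identical. No arm has one without the other, so the two are fully aliased and covariate adjustment cannot separate them. Gamification against plain a-DOT does not help, because both arms receive the tiers. That TAU receives no tiered cash is inferred from B.9.6 limiting it to the a-DOT arm; no sentence says so outright.

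**2. Size of the cash contrast.** Inputs:
- tiers, visit and pack payments from B.9.6;
- follow-up research visits at weeks 4, 8 and 12 (B.9.2);
- a baseline research visit, which B.8 confirms (subjects "will be instructed on using the a-DOT platform at the baseline research visit");
- six biweekly packs over 12 weeks.

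Tiers are read as the highest one reached, not cumulative.

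- Tiered cash: 3 × 30 = USD 90 per a-DOT subject, against 0 in TAU. It would be 4 × 30 = USD 120 if a week-16 visit counted.
- TAU maximum: 4 × 25 + 6 × 10 = USD 160.
- Plain a-DOT maximum: 160 + 90 = USD 250. Ratio: 90/160 = 56% more.
- If the baseline visit is not paid: 3 × 25 + 60 = USD 135 against USD 225, and 90/135 = 67% more.

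B.9.6 gives an overall ceiling of USD 453 including metrocards, whose value is not stated, so it cannot be reproduced exactly. For a gamification subject who wins the top prize at three visits, the described items sum to 250 + 3 × 50 = USD 400. That fits under the ceiling.

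**3. What the a-DOT versus TAU contrast estimates.** It is the effect of app and cash together. B.10 assumes 80% adherent against 50%, a 30-point difference. The documents give no effect of cash alone, so the following is an illustration under assumed values only. If cash alone moved TAU from 50% to 60%, 20 points would remain for the app; if to 70%, 10 points would remain.

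**4. What it costs to drop the gamification arm from the contrast.** Assumptions: two-sided 5%, one binary outcome, 50% against 80%. Pooled-z power is Φ[(0.30 − 1.96·SE₀)/SE₁].

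- 25 v. 25: SE₀ = √(0.65 × 0.35 × 2/25) = 0.1349; SE₁ = √(0.25/25 + 0.16/25) = 0.1281; power = Φ(0.278) = 60.9%. Fisher exact by enumeration: 51.0%.
- 25 TAU v. 50 a-DOT: SE₀ = √(0.70 × 0.30 × (1/25 + 1/50)) = 0.1122; SE₁ = √(0.25/25 + 0.16/50) = 0.1149; power = Φ(0.696) = 75.7%. Fisher exact: 69.1%.
- 95% CI half-width, 1.96·SE₁: 25.1 points against 22.5 points.

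This is not the planned repeated-measures model. With three visits, intraclass correlation 0.5 and design effect (1 + 2 × 0.5)/3 = 0.667, pooled-z power is 78.9% for 25 v. 25 and 90.0% for 25 v. 50.

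**The case against.** The strongest reply is that nothing is hidden. B.9.6 ties the tiers to the randomized arm, so the a-DOT strategy visibly includes them, and a package intervention is legitimate. The comparison of package with TAU is valid. That stands, and it is why the remedy is mainly wording. It does not rescue the attribution, because the arm definitions, the hypothesis and the analysis, which determine what is concluded, all omit the cash.

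Other points have partial force:

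- **SVR.** The plan concedes low power and calls itself a pilot. Most of its SVR analysis is a single-group proportion and a historical comparison. But the caveat concerns power, not what the effect consists of, and the pilot's stated product is an effect size for later studies.
- **The later trial.** Nothing says that it would drop payment. If it keeps the tiers, the package effect is the right input, which is a reason to label it as such.
- **The percentage.** The 56% describes maximum pay and is not a measure of bias. The useful figure is up to USD 90 against none.
- **Pooling.** B.9.6 and B.10 both treat the a-DOT arm as n=50, so pooling is strongly implied, though not stated for the adherence test. If the arms are pooled, rank prizes also enter the contrast.
- **Scoring of tiers.** Table 3 makes pill count the natural reading, while the tie-break on dosing time in B.9.6 points to dashboard data for the prizes. The pack-emptying concern remains conditional.
- **Separating the two.** Only identical payment terms in all arms, or a-DOT without the tiers, would do so. That is a design change, and paying TAU would alter what usual treatment means.

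**Conclusion.** The concern holds and should be fixed. App and adherence-contingent cash are fully aliased in a-DOT versus TAU. The trial can estimate a-DOT plus payment against TAU without such payment, and it cannot attribute an adherence or SVR difference to a-DOT alone. The cash contrast is up to USD 90 per subject over a 12-week course, on the reading that tiers are not cumulative and that TAU receives none. How much of any observed difference is due to cash cannot be stated from the documents. Differential distortion of pill counts is a possibility only if pill count scores the tiers.

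**What to change.** **Essential, wording only; the price is a narrower claim.**

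1. In Aim 1, B.8 and B.10, define the intervention as a-DOT plus adherence-contingent payment, and the control as TAU without such payment.
2. In B.10, including the sentence on the effect size for later studies, limit the conclusion and any effect size carried forward to that package. Add: *The effect of a-DOT without payment is not estimated in this trial.*

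**Supplementary.**

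3. Report plain a-DOT (n=25) against TAU (n=25) alongside the main comparison. This removes the rank prizes but not the tiers. On the single-outcome calculation it costs about 15 points of power by pooled-z (75.7 − 60.9) or 18 by Fisher exact (69.1 − 51.0), and widens the CI half-width from about 23 to 25 points. It should not replace the main comparison.
4. State which measure scores the tiers. If it is pill count, acknowledge the one-sided cash motive and check a-DOT subjects' pill counts against the dashboard. B.10 now plans agreement only between pill count and self-report, but B.2 already provides the data: "We will measure adherence with pill counts in both arms and with the a-DOT interface in the a-DOT arm". The cost is one added agreement analysis.

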B.9.2. Research visits. Research visits will occur every 4 weeks during the 12 - 16 weeks of treatment. Participants will receive \$25 for each research visit and an additional \$10 for each returned biweekly pack.

Baseline visit (Table 3). At baseline we will conduct chart review using standardized tool (Protocol: “HCV Clinical Registry”).

Follow-up visits (Table 3). Follow up visits will occur at weeks 4, 8, 12, and 16 (if necessary). Adherence to all medications will be evaluated by pill counts. Weeks on treatment will be determined by chart review (including pharmacy database). HCV viral load and virological endpoints (see below) will be obtained by chart review.

Table 3. Overview of Data Collection by Aims				
Aim & Hypothesis	Construct	Measure	Research visit (week)	Source
Outcome Measures				
All	Adherence	Pill count	4,8,12	RA
All	Completion	≥ 80% of planned treatment duration	NA	Chart and Pharmacy Database
All	Viral Load	Roche TaqMAN assay	0, 4, 8, 12, follow up 4, follow up 12	Chart
Other covariate measures*				
All	Demographics	Age, race/ethnicity	0	Chart
All	HCV-related clinical information	HCV VL, HIV, HCV genotype/subtype, IL28B, APRI and FibroSURE (biomarkers of liver fibrosis), liver tests (AST, ALT, total bilirubin, direct bilirubin, albumin), PT/INR, liver biopsy (if available), and fibroscan	0	Chart
All	Substance use	Urine toxicology	0,4,8,12	Chart
All	Addiction treatment	Methadone or buprenorphine dose (if applicable)	0,4,8,12	Chart

B.9.3. Definitions of outcome measures.

AICure missed dose adherence. For Zepatier, adherence will be calculated based on pills left in Med-ic blister pack where X=number of blisters with missing doses and Y=14. If packs are not brought back for pill count, we will assume conservatively that X=0, and also impute adherence based on other time periods in which packs have been returned (total of 6 – 8 observation periods).

HCV treatment completion. Subjects will be considered to have completed treatment if they have completed at least 80% of the planned treatment course (e.g. at least 10 weeks of 12 week course)

Sustained viral response (SVR). SVR is defined as undetectable HCV viral load 12 weeks after treatment completion or discontinuation.

B.9.4. Data Sources. There will be four data sources: medical record, pharmacy database, pill counts, and a-DOT dashboard,

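### Only the a-DOT arms are paid for adherence, and as most naturally read the payment rests on the pill count that is also the trial's adherence outcome

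*Combined protocol and SAP*

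**What the plan says.** **Who is paid.** B.9.6: "Subjects randomized to the a-DOT arm (n=50) will receive additional incentives based on adherence measured at monthly visits". The first step is 10 dollars "for 50% adherence", followed by 20 dollars at 80% and 30 dollars at 95%. In the gamification arm, "the second-most adherent participant will receive an additional" 35 dollars and the first-placed participant 50 dollars. All arms receive 25 dollars per visit and 10 dollars "for each returned blister pack", whatever the pack contains. No payment tied to adherence level is described for TAU.

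**What is measured at those visits.** B.9.2: "Adherence to all medications will be evaluated by pill counts". Table 3 lists the pill count at weeks 4, 8 and 12, with the research assistant as source, and no other adherence measure.

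**What the outcome is.** B.9.3: "adherence will be calculated based on pills left in Med-ic blister pack", as emptied blisters out of 14 per biweekly pack. B.10 analyses adherence as a percentage and at a cut of 80% or more, using pill count and self-report.

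**What the prizes rest on.** Aim 3: "Those with highest levels of adherence measured at monthly research visits compared to their peers will earn additional incentives". B.8, for the same arm: "subjects will receive real-time feedback regarding ranking of their adherence to Zepatier". B.9.6 breaks a tie for first place by time of dosing.

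**The concern.** A pill count records that a blister is empty, not that the tablet was swallowed. That weakness is tolerable in a comparison when it is the same in every arm. Here, as most naturally read, a-DOT subjects earn more for emptier packs and TAU subjects do not, so any over-counting would be differential and would favour a-DOT. The 20-dollar step lies on the 80% cut that defines an adherent subject.

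This is a measurement problem, distinct from whether cash is a legitimate part of the intervention. Even if it is, the outcome has to mean the same thing in all arms. At stake is the adherence comparison in Aim 1, which is what the power statements in B.10 address, and, if the prizes also rest on the pill count, the gamification comparison in Aim 3.

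**Working it through.** The plan states no figure for this point, so the check is first a comparison of passages and then an illustration.

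**1. Is the payment basis the outcome?**
- Graded payments: B.9.6 refers to adherence measured at monthly visits; B.9.2 and Table 3 schedule only the pill count there; B.9.3 and B.10 make that count the outcome. This chain is an inference, but the natural one.
- Prizes: Aim 3 points to the monthly visits. The real-time ranking (B.8) and the dosing-time tie-break (B.9.6) need data that a monthly blister count, as defined, does not give. The prize basis is therefore unresolved.

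**2. Would a planned analysis show topping-up?** B.10 compares pill count with self-report. A subject who empties blisters for payment has no reason to self-report otherwise. Dashboard adherence is collected in the a-DOT arms (B.2, B.9.4), but no analysis in B.10 uses it. SVR cannot be raised by emptied blisters, but B.10 concedes that the study lacks power for it.

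**3. How close are the steps?** A month is two packs of 14, so 28 tablets.

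| Emptied | Monthly count | Payment | Against 80% |
|---|---|---|---|
| 22/28 | 78.6% | 10 dollars | below |
| 23/28 | 82.1% | 20 dollars | above |
| 27/28 | 96.4% | 30 dollars | above |

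One blister moves a *month* across the cut. It does not move the 12-week classification in B.10: a subject at 22/28 each month has 66/84 = 78.6%, one more gives 67/84 = 79.8%, and two more are needed for 68/84 = 81.0%.

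**4. Illustration, binary outcome.** Assumptions, not in the documents: no true effect; 50% truly adherent in both groups (50% is the plan's TAU rate in B.10); a fraction g of non-adherent a-DOT subjects tops up past 80%. The observed a-DOT rate is 0.50 + 0.50 × g. Rejection probabilities come from exact enumeration of the two binomials, 50 v 25, two-sided 5%.

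| g | Observed a-DOT v TAU | Chi-square | of which favouring a-DOT | Fisher |
|---|---|---|---|---|
| 0 | 50% v 50% | 6.0% | 3.0% | 4.1% |
| 0.20 | 60% v 50% | 14.7% | 14.4% | 11.1% |
| 0.30 | 65% v 50% | 25.8% | 25.8% | 20.5% |

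**5. Illustration, continuous outcome.** B.10 gives pilot SDs of 12% (n=21) and 20% (n=19). The pooled SD is √[(20×12² + 18×20²)/38] = 16.3 points, so the 10-point difference is d = 10/16.3 = 0.61, which agrees with the plan's 0.6. Ten points is 0.10 × 28 = 2.8 blisters a month. Each blister emptied without ingestion adds 1/28 = 3.6 points. Taking the mean of three monthly counts at ICC 0.5 (variance factor (1 + 2×0.5)/3 = 0.67) and a t-test at 50 v 25, an assumed average of 1, 2 or 3 such blisters a month in the a-DOT arms alone gives significance in 19%, 58% or 90% of trials, against 5% with none.

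**The case against.** **The payment source is never named.** The a-DOT arms have a second measure, the app, and B.8 speaks of incentives collected at the monthly visits, which may make the visit only the time of payment. B.9.3 even heads its blister-count definition with the app vendor's name. If payment comes from the app, a blister emptied off camera earns nothing and the mechanism largely fails. This stands. A reader might infer that the protocol definitely pays both steps and prizes on the pill count. The documents do not support that: for the steps it is the natural reading, and for the prizes the text conflicts.

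**Topping-up would be noticed.** A dose not taken within 2 hours brings a reminder, and within 4 hours a staff call (B.8). This makes the behaviour harder to hide, but does not correct the pill count or enter the analysis.

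**The illustration is not the planned analysis.** B.10 plans mixed-effects models for the repeated measures, and nothing in the documents supports 20%, 30% or any other top-up rate. Both points stand. It would also be wrong to read 15% as 15 points of excess error, since the same test rejects in 6% with no shift, or to say that one blister makes a subject adherent over 12 weeks.

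**This is a pilot meant to inform later studies.** True, but its adherence effect sizes are what those studies would use, and a differential measurement error would carry over into them.

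**Conclusion.** The point holds in conditional form. Adherence pay exists only in the a-DOT arms, one step coincides with the outcome's 80% cut, and the only adherence measure scheduled at the paid visits is the outcome itself. On that reading the a-DOT v TAU pill-count contrast can be biased upward without ingestion, undetected by the planned analyses. Bias in Aim 3 follows only if the prizes are also awarded on the pill count. The direction follows from the design; the size does not. The 15% and 26% (against 6%) rest on assumed top-up rates and a simple chi-square test. Nothing in the documents shows that subjects would in fact top up, although B.1.1 describes cheating patterns that the app detected in earlier medication trials. The change is worth making because it uses data already collected.

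**What to change.** - **B.9.6 and Aim 3:** state that graded payments and prizes are based on doses confirmed on the a-DOT dashboard since the last visit. This also removes the conflict between Aim 3, B.8 and B.9.6.
- **Consent and instructions:** tell subjects that the pill count does not affect payment.
- **B.9.3:** keep the returned-pack pill count as the unpaid outcome in all three arms.
- **B.10:** in the a-DOT arms, report dashboard minus pill-count adherence as a check for emptied blisters.
- **Report:** say that the a-DOT effect includes the cash incentives. The changes above do not separate the cash from the app.

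The cost is wording and one descriptive analysis. There are two downsides. A real dose that the app fails to confirm could cost a subject money; the stored audit trail described in B.1.1 can be checked before payment. Any incentive to cheat also moves to the app, which is designed to detect it but not perfectly: B.1.1 reports step accuracies of 97.3% to 98.9%.
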